26.0 Specimen Use and Banking

26.1 Tear samples will be stored at College of Optometry, JDA building until batch analysis.

26.2 The samples will be stored until analysis.

26.3 Only the investigators in this study will have access to the specimens.

26.4 The investigators in this study will be responsible for the transportation of the specimens from Health 1 to JDA building in College of Optometry.

26.5 The samples will be transported in a triple sealed container on ice.

26.6 Tear samples will be stored in the lab until analyses.

26.7 There will not be enough specimens to save or store for future use.

27.0 Community-Based Participatory Research

N/A

28.0 Sharing of Results with Subjects

28.1 Subjects will be unmasked at the end of the study and informed of their contact lens parameters. The subject may choose to share this information with their eye doctor to inform future contact lens fitting needs.

29.0 Resources

FULL PROTOCOL TITLE: Toric Contact Lens Digital Performance and Comfort Study

29.1 The study team completed all necessary ethics training requirements. The PI ([name]) has nearly two decades of experience conducting clinical care and research and will oversee all study personnel.

29.2 With an abundance of contact lens wearers in the surrounding community, and based on our recruitment with previous contact lens studies we believe that we should be able to complete enrollment within 6-9 months.

Title

Toric Contact Lens Digital Performance and
Comfort Study

NCT number

NCT04772560

Document date

20 Dec 2021

Statistical Plan

The outcome measures for the two contact lens designs were first analyzed using the Grizzle model. The data were tested for the presence of a carry-over effect by examining the average of outcomes in the two periods within subjects between the two sequences of randomization, that is, sphere then toric / toric then sphere. Independent paired T-test or Mann-Whitney test, as appropriate, was carried out to ensure there were no carry-over or period effects at the alpha level of 0.10.¹⁹ The differences in outcome measures between lens designs were examined using a linear mixed model, with fixed factors of sequence and contact lens design to obtain unbiased effect sizes. Estimated means, standard errors and medians and interquartile ranges were reported for each lens design. Estimated means, standard errors, and 95% confidence intervals of the differences between lens designs were also reported. In the presence of any carry-over effects, hypothesis tests were conducted on period one only. Significance was defined as P values of 0.05 or less.

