5.0 Number of Subjects

5.1 The proposed single-site study will be conducted at the University of Houston College of Optometry. Up to 30 subjects will be screened for study inclusion, with the goal of completing 24 subjects.

Source data will be collected on paper case report forms and then double entered electronically into a database by trained personnel prior to locking the dataset for analysis.

5.2 In this within-subject crossover design, a paired T-test will be used to compare visual acuity performance, contact lens discomfort, subjective visual quality and LTB4 concentration following toric lens wear to spherical contact lens wear. We will use a two-sided independent T-test to ensure there are no carry over or period effects in our cross-over design, although it is not anticipated. As a secondary outcome, subjects will be asked their preference of contact lenses in a two-alternative forced choice format.

FULL PROTOCOL TITLE: Toric Contact Lens Digital Performance and Comfort Study

One-sample binomial tests will be used to test the hypothesis that the probability of preference to toric lens and spherical lenses are equally likely. Linear mixed model or generalized linear model, as appropriate, will be carried out to examine the associations between eye comfort, visual performance, subjective visual quality and LTB4 concentration during toric and spherical contact lens wear.

We aim to test the hypothesis that $H_0: \Delta=0$ v. $H_1: \Delta \neq 0$ using a two-sided test with significance level $\alpha=0.05$, where Δ is the underlying benefit for treatment contact lenses versus spherical contact lenses in this cross-over design. Our previous work found that toric correction improved visual acuity compared to spherical correction by 6 and 11 letters for high and low contrast logMAR, respectively ($P < 0.001$).¹⁰ To demonstrate an improvement of this amount or more it will require at least 24 and 15 subjects with a $P=0.05$ and 80% power. The dynamic visual acuity test is novel and has not been used previously to allow sample size estimates. A total of 30 subjects will be enrolled to allow for up to 20% dropout/screen-failure/missing data and have 24 subjects complete. We will randomize an equal number of subjects to each group (i.e., group A receives treatment 1 in period 1 and treatment 2 in period 2; group B receives treatment 2 in period 1 and treatment 1 in period 2).

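### The SAP names no variable for its period test; if it used the two-period averages named for carry-over, it could not detect a period effect, and the mixed model does not adjust for one

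*SAP*

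**What the plan says.** The SAP's Statistical Plan says the outcomes "were first analyzed using the Grizzle model". It then says "The data were tested for the presence of a carry-over effect". The variable given for that check is a mean over both periods, set against randomization order: "examining the average of outcomes in the two periods within subjects between the two sequences of randomization". The next sentence names the procedure and widens its purpose: "Independent paired T-test or Mann-Whitney test, as appropriate, was carried out to ensure there were no carry-over or period effects". The alpha for this step is 0.10.

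The lens comparison is a linear mixed model "with fixed factors of sequence and contact lens design to obtain unbiased effect sizes". Period is not listed. One follow-up action is given, and it concerns carry-over only: "In the presence of any carry-over effects, hypothesis tests were conducted on period one only".

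Protocol section 5.2 makes the same double claim without naming a variable: "We will use a two-sided independent T-test to ensure there are no carry over or period effects in our cross-over design".

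**The concern.** A carry-over test and a period test in a two-period crossover need different variables. Carry-over is examined on the subject's average (or sum) over the two periods, and period on the within-subject difference. The SAP describes the first, mentions no difference in this preliminary step, and credits one procedure with excluding both effects. It also calls the t-test both independent and paired, which no t-test can be, so the text does not settle what was run.

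A shift between Visits 3 and 5 is plausible. Near acuity, Radner reading, dynamic acuity and the iPad functional test are all repeated at Visits 1, 3 and 5 (Protocol section 10.3, table of visit procedures), and section 5.2 calls the dynamic acuity test novel. If the check cannot see such a shift and the model does not adjust for it, readers would take the toric-sphere estimates as checked for period when they were not.

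**Working it through.** **Inputs from the documents.** Two-period crossover with 1:1 allocation, 30 enrolled, 24 completers, so 12 per sequence if losses are even (Protocol 5.2). Preliminary alpha is 0.10 (SAP), taken as two-sided from the Protocol. The model's fixed factors are sequence and lens design (SAP).

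**The plan's own figure.** 24 / (1 − 0.20) = 30, which reproduces the planned enrolment. The 24 subjects for a 6-letter difference cannot be reproduced forward because no SD is given. Solved backwards for a paired comparison (two-sided 0.05, 80% power), the SD of the difference is 6 × √24 / (1.960 + 0.842) = 10.5 letters by the normal formula, or 10.0 by the t distribution. A lens effect of 6/10.0 = 0.6 SD is therefore the size the plan implies; it is an inference, not a stated value.

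**Test on averages.** Write π1 and π2 for the period effects, τT and τS for the lens effects, and λT and λS for carry-over from each lens into period 2.

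- Toric first: μ + (π1+π2)/2 + (τT+τS)/2 + λT/2
- Sphere first: μ + (π1+π2)/2 + (τT+τS)/2 + λS/2
- Difference between sequences: (λT − λS)/2

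The period terms cancel whatever the variances. Simulation agrees (40,000 trials, 12 per sequence, within- and between-subject SD both assumed to be 1). At period effects of 0, 0.25, 0.5, 1, 2, 5 and 10 within-subject SDs, the t-test on averages rejected in 9.8% to 10.1% of trials. Mann-Whitney on averages (4,000 trials) gave 9.8% to 10.6%. The same t-test does respond to carry-over: 25%, 62% and 99.9% at differential carry-over of 1, 2 and 5 SD.

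**Test on differences.** Let π = π2 − π1 and τ = τT − τS, with no carry-over. Toric-minus-sphere differences have expectation τ − π (toric first) and τ + π (sphere first), so the contrast between sequences is 2π. With 12 per sequence and alpha 0.10, a two-sample t-test rejects in about 32%, 77%, 97% and over 99% of trials at shifts of 0.25, 0.5, 0.75 and 1.0 SD of the within-subject difference. In units of the within-subject SD of a single measurement, power at a 0.5 SD shift is about 51%.

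**If paired means Visit 5 against Visit 3.** This test responds to period, but the lens effect inflates its error and enters its estimate when sequences are unequal. With an assumed lens effect of 0.6 SD, it rejects at shifts of 0.25 and 0.5 SD in about 23% and 67% of trials with 12/12 completers, 12% and 49% with 14 toric-first and 10 sphere-first, and 40% and 82% with the reverse split.

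**Effect on the lens estimate without a period term.** With n1 toric-first and n2 sphere-first completers, the expected estimate is τ − π(n1 − n2)/(n1 + n2).

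| Completers (toric first / sphere first) | Movement of the lens estimate |
|---|---|
| 12/12 | 0 |
| 13/11 | −(2/24)π = −0.08π |
| 14/10 | −(4/24)π = −0.17π |
| 10/14 | +0.17π |

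**Effect on power at 12/12** (SD of the difference 1, lens effect 0.6 SD, two-sided 0.05). The unmodelled shift inflates the SD of the differences to about √(1 + π² × 24/23). Power is roughly Φ(0.6√24 − 2.069 × SD), where 0.6√24 = 2.939.

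- π = 0: SD 1.00, Φ(0.87), about 80% exactly
- π = 0.5: SD 1.12, Φ(0.62), about 73%
- π = 1: SD 1.43, Φ(−0.02), about 50%

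With period in the model the SD stays at 1 and the critical value becomes 2.074 on 22 degrees of freedom. Φ(2.939 − 2.074) = Φ(0.865), so power stays near 80% at every shift.

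**The case against.** The strongest reply is that the SAP never says period was tested on the averages. It ties the average to carry-over alone, and the next sentence names a family of tests without a variable for period. The Grizzle model it cites allows a separate period test on within-subject differences, and the sentence carries a reference that is not among the documents. The Protocol's independent t-test, or the SAP's Mann-Whitney alternative, would be the right procedure if applied to differences, and the word paired may be a drafting slip. This stands. A reader might infer that the wrong period test was certainly run, but the documents do not support that.

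The harm is also bounded. Allocation is equal, and with equal completers there is no bias. The novel iPad tests are secondary endpoints; the primary endpoint is near visual acuity (Protocol 9.1). All these tests are also done at Visit 1, a practice run that may shrink any later shift.

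What does not stand is the suggestion that the text is therefore adequate. No variable for period is stated, one self-contradictory procedure is said to exclude both effects, and no later step adjusts for period. Equal completers are not guaranteed when up to 20% loss is planned for.

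**Conclusion.** The concern holds in conditional form. If the preliminary test used the averages, its power for a period effect equals its alpha of 10% at any shift, so a conclusion of no period effects would be unsupported. If another variable was used, the SAP does not say so. In both cases the mixed model leaves the lens estimate unadjusted for period.

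The cancellation is exact under the additive crossover model and needs no variance assumption. The consequences do rest on assumptions. The power loss (80% to 73% or 50%) assumes a 0.6 SD lens effect, 12/12 completers and shifts of 0.5 or 1 SD of the within-subject difference. The movement of 0.17 of the shift assumes a 14/10 or 10/14 split. The documents state none of these values, and they give no evidence that a shift occurred.

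A reader might also infer that the toric-sphere estimates are biased. That does not follow: with equal completers the bias is zero, and with unequal completers it is a small fraction of the shift and can go either way. The change should be made because the written plan does not support the claim and the repair is nearly free.

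**What to change.** - Add period as a fixed factor to the mixed model, beside sequence and lens design, and report the period estimate with its 95% CI for each outcome. This removes the imbalance bias and restores the lost precision; a further preliminary test would do neither.
- If a preliminary period test is kept, state its variable: toric-minus-sphere differences compared between sequences by an independent two-sample t-test, or Mann-Whitney where appropriate.
- Keep the test on averages for carry-over only, and delete the word paired.
- Do not claim absence of period effects from the test on averages, or from non-significance alone. With 24 completers even the correct test has only about 51% power at a shift of 0.5 within-subject SD.
- If a difference-based test was in fact run, describe it.

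The cost is one degree of freedom, a rewritten sentence and a refit to data already held. A practice effect may then have to be reported.

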9.2 This is a minimal risk study so safety endpoints are not required

10.0 Procedures Involved

10.1 The study is a clinical trial and will be registered on ClinicalTrials.gov prior to subject enrollment.

10.2 Patients will be seen for 5 visits over a period of approximately 1 month. Visit 1 will determine subject eligibility for the study. Visits 2 and 4 are contact lens follow-up visits. Visits 3 and 5 are study outcome visits. Tests of visual performance at a near reading distance will be evaluated with an iPad application developed by [name]. These applications are designed for research purposes only and are not commercially available. The applications can measure reading speed and provide information on how a subject interacts with the electronic device (e.g. blink rate, working distance from the device, scrolling and zooming on the page, etc.).

10.3 Subjects will be randomized to start with either toric lenses or spherical correction (FDA approved lenses will be utilized).

Overview of Visit Procedures (Assessments)

FULL PROTOCOL TITLE: Toric Contact Lens Digital Performance and Comfort Study

A masked examiner will perform all outcome measures.

| | Visit 1 Baseline and Fit Lens 1 | Visit 2 day 3±1 | Visit 3 – day 10±2 | | Visit 4 day 13±1 | Visit 5 day 20±2 |
|--|--|-------------------------|-----------------------|---------------|-------------------------|---------------------|
| | | Follow- up Lens 1 | Outcomes Lens 1 | Fit Lens 2 | Follow- up Lens 2 | Outcomes Lens 2 |
| Informed consent | X | | | | | |
| Ocular/medical/contact lens history | X | | | | | |
| Ocular symptoms (CLDEQ-8) ⁸ | X | | X | | | X |
| Auto-refraction and keratometry | X | | | | | |
| Slit lamp exam with NaFl staining | X | | | | | |
| Manifest refraction | X | | | | | |
| Accommodation and phoria | X | | | | | |
| Near logMAR HCHL & LCHL acuity OU | X | | X | | | X |
| NAVQ survey ⁵ | X | | X | | | X |
| Radner reading sentences, dynamic acuity measurement and functional vision test with iPad ⁴ | X | | X | | | X |
| Tear collection | X | | X | | | X |
| Study lens order randomization | X | | | | | |
| Insertion of CL and settling (15 min) | X | | | X | | |
| Clinical CL vision and fit assessment, over-refraction, and power adjustment if indicated | X | X | | X | X | |
| Removal of study lens and slit lamp exam with NaFl staining | | X | X | | X | X |

FULL PROTOCOL TITLE: Toric Contact Lens Digital Performance and Comfort Study

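### The SAP's mixed model for the lens difference omits period, and neither the Grizzle step nor the period test is tied to the reported estimates; the likely cost is a small loss of precision

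*SAP*

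**What the plan says.** The SAP (Statistical Plan) sets out these steps:

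- **First step.** "The outcome measures for the two contact lens designs were first analyzed using the Grizzle model".
- **Pre-test.** A two-group comparison "was carried out to ensure there were no carry-over or period effects at the alpha level of 0.10".
- **Lens difference.** A "linear mixed model, with fixed factors of sequence and contact lens design to obtain unbiased effect sizes". Period is not among the listed fixed factors.
- **Reporting.** Estimated means, standard errors and 95% confidence intervals of the lens differences come next in the text. The model that supplies them is not named.
- **Action rule.** "In the presence of any carry-over effects, hypothesis tests were conducted on period one only". No action is stated for a period effect.

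The protocol (section 5.2) is simpler: "a paired T-test will be used to compare visual acuity performance" and the other lens comparisons. It also plans a test for carry-over or period effects, "although it is not anticipated". Allocation to the two sequences is equal. Lens preference is handled separately, as a forced choice with a binomial test.

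**The concern.** A 2×2 crossover measures each subject once per period, so a general change between the two outcome visits (practice, adaptation, calibration drift) enters every paired difference. It enters with one sign for subjects who start in spheres and the opposite sign for those who start in torics. A period term removes it. A sequence term cannot, because sequence is constant within a subject.

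The SAP's stated aim is an unbiased effect size, yet the listed model leaves out the factor specific to this design. The steps that do look at period do not feed the reported estimate. If P values came from the Grizzle step and intervals from the mixed model, the two could disagree.

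What is at stake is mainly precision. The completer target of 24 is set at 80% power for the 6-letter high-contrast difference, with no stated reserve among completers.

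**Working it through.** **Inputs from the documents.** Two-sided alpha 0.05; 80% power; 24 completers for 6 letters and 15 for 11 letters; 20% loss; 1:1 allocation (protocol 5.2). Outcome visits are on day 10 ± 2 and day 20 ± 2 (protocol 8.1).

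**Plan's own figures.** 24/(1 − 0.20) = 30 reproduces the enrolment target. The 24 and 15 cannot be reproduced, because no SD is given. By noncentral t, 80% power with 24 pairs needs a standardised effect of 0.597. That implies an SD of the paired difference of 6/0.597 = 10.05 letters. The 11-letter, 15-subject statement implies about 14.1 letters. I therefore work in SDs of the paired toric-minus-sphere difference, and use 10 letters only to translate.

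**Assumed period shift π.** 0.1 to 0.25 SD as plausible, and 0.5 SD (about 5 letters, close to the whole 6-letter lens effect) as an upper end.

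**Step 1: sequence does not absorb period.** In this design, period is the sequence-by-lens interaction. The design matrix has rank 3 with intercept, sequence and lens, and rank 4 once period is added.

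**Step 2: what the listed model estimates.** Let d be toric minus sphere and τ the lens effect. Then E[d] = τ + π if sphere is first and τ − π if toric is first. With complete pairs and a random subject effect, the model returns the mean of d, so

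estimate = τ + π(n_ST − n_TS)/N.

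As a check on one simulated 14/10 data set, lens + sequence gave 0.7050 (SE 0.1767), equal to the paired t-test. Adding period gave 0.6908, the half-sum of the two sequence means.

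At 14/10 the realized shift is π × 4/24. With SD 10 letters that is 0.2, 0.4 and 0.8 letters for π = 0.1, 0.25 and 0.5 SD, in either direction.

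**Step 3: precision at 12/12.** Without period the expected variance estimate is SD²(1 + π²·N/(N − 1)), with π in SDs, on N − 1 df. With period it is SD² on N − 2 df. The interval-width ratio is t(0.975, 23)·√(1 + π²·24/23) / t(0.975, 22), where t(0.975, 23)/t(0.975, 22) = 1/1.00252.

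| π (SD) | CI width, without/with | Power without | Power with | Type I error without |
|---|---|---|---|---|
| 0.1 | 1.003 | 79.7% | 79.9% | 4.9% |
| 0.25 | 1.03 | 78.1% | 79.9% | 4.4% |
| 0.5 | 1.12 | 72.4% | 79.8% | 2.9% |

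Power and type I error are simulated.

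**Step 4: average over completing splits.** The number randomized is not fixed by the text: "A total of 30 subjects will be enrolled to allow for up to 20% dropout/screen-failure/missing data", and "Visit 1 will determine subject eligibility for the study", so some of the 30 may fail screening before randomization. I take 24 to 30 randomized and 24 completing, with losses at random (hypergeometric). A split of 14/10 or worse has probability 0% if 24 or 26 are randomized, 10% if 28 and 17% if 30.

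| Randomized | Power with period | Without, 0.1 SD | Without, 0.25 SD | Without, 0.5 SD |
|---|---|---|---|---|
| 24 | 79.8% | 79.8% | 78.3% | 72.5% |
| 26 | 79.7% | 79.7% | 78.1% | 72.3% |
| 28 | 79.6% | 79.7% | 78.1% | 72.1% |
| 30 | 79.5% | 79.7% | 78.0% | 72.0% |

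Differences of 0.1 to 0.2 points are within simulation and rounding error.

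**Step 5: can the pre-test stand in for the term?** At alpha 0.10 and 12/12, the period test has power of about 14% at 0.1 SD, 33% at 0.25 SD and 77% at 0.5 SD. A null result would therefore not justify leaving period out.

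**The case against.** The strongest case against the point is that it changes very little.

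- **Period is not ignored.** A Grizzle analysis normally carries a period term, the SAP tests period, and the protocol expects no effect. This stands. The gap is that neither step is linked to the reported differences. If they did come from the Grizzle step, one sentence would settle it.
- **A large shift is unlikely.** The outcome visits are about 10 days apart, and the same near acuity, reading and dynamic acuity tests are scheduled at Visit 1 (procedures table, protocol section 10), which may use up much of any practice effect. This is why 0.5 SD is only an upper-end assumption.
- **Omitting period can be no worse.** At 12/12 the two models break even at a shift of about 0.07 SD. By interval width the break-even rises to 0.10 SD at 13/11 and 0.18 SD at 14/10. Averaged over splits, the models tie at 0.1 SD. This stands too.
- **The SAP's claim of unbiasedness is defensible.** Under 1:1 randomization with loss unrelated to sequence, the expected shift of the estimate is zero. What remains is a fraction of a letter in one realized trial.

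A reader might infer that the omission makes a false toric benefit more likely. The design does not support that. Type I error without period is at or below 5% for splits from 12/12 to 14/10. It can pass 5% slightly only at 15/9, which has 1.7% probability with 30 randomized, too little to lift the average above 5%.

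**Conclusion.** The point holds as a minor one. The listed model omits period, sequence cannot replace it, and the SAP does not connect its Grizzle step or period test to the estimates it reports.

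Over the plausible range the cost runs from nothing measurable (0.1 SD) to about 1.5 to 1.7 points of power and a 3% wider interval (0.25 SD). At the upper-end 0.5 SD it is about 7 points (79.8 − 72.5 = 7.3 with 24 randomized; 79.5 − 72.0 = 7.5 with 30) and a 12% wider interval. The error is overall on the conservative side. With unequal completing sequences a single trial's estimate also moves slightly, in an unpredictable direction.

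This rests on 24 complete pairs, losses unrelated to sequence, and an assumed period shift and SD. The documents give neither, so they do not show that this trial actually lost power, only that its listed model offers no protection if a shift occurred.

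**What to change.** For every outcome analysed by the mixed model, fit lens + period + sequence with a random subject effect. Report the period-adjusted lens difference with its 95% confidence interval, together with the period estimate. State that the period pre-test does not decide whether the term stays in, and name the model that supplies the reported differences. Lens preference is outside this change: it is a single forced choice per subject, with no per-period observation to model.

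The SAP is dated 20 Dec 2021 and written in the past tense. If the analyses are done, re-fit on the existing data and show the result beside the original estimate.

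No new data are needed, since period is known for every observation. The cost is one degree of freedom. With no true period effect, power falls by about 0.2 points at 12/12, 0.4 at 13/11 and 1.3 at 14/10.

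### Pre-testing carry-over at 0.10 and falling back to period one lifts the lens comparison's type I error from 5% to about 7–9% and costs power

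*SAP*

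**What the plan says.** The SAP (Statistical Plan) names the Grizzle model. Carry-over is assessed by "examining the average of outcomes in the two periods within subjects between the two sequences of randomization", using a t-test or Mann-Whitney test that "was carried out to ensure there were no carry-over or period effects at the alpha level of 0.10". The lens comparison itself uses a "linear mixed model, with fixed factors of sequence and contact lens design". The fallback is: "In the presence of any carry-over effects, hypothesis tests were conducted on period one only". One level is given for all hypothesis tests: "Significance was defined as P values of 0.05 or less". Nothing adjusts that level for the data-driven choice between the two analyses.

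The SAP does not say outright that p<0.10 triggers the fallback, but 0.10 is the only level it attaches to this test.

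Protocol section 5.2 plans a paired t-test and sizes the trial on it: 24 completers for 6 letters of high-contrast acuity, 80% power, two-sided 0.05. It also says: "We will use a two-sided independent T-test to ensure there are no carry over or period effects in our cross-over design". It adds that carry-over is not expected. It gives no 0.10 level and no period-one fallback.

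**The concern.** This is the classical two-stage crossover procedure, and it has two weaknesses.

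First, the two stages are not independent. A subject's average contains the period-one value, and both tests compare the same two groups of people. If one sequence happens to contain people with better acuity, the carry-over test is flagged, and the analysis then moves to the comparison that this imbalance distorts most. That comparison is still judged at 0.05.

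Second, the pre-test is a between-subject test with about 12 people per sequence. It cannot do what both documents ask of it, which is to establish that carry-over is absent.

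The stated 5% error rate and 80% power for the primary endpoint are therefore not those of the procedure as written. Applied outcome by outcome, the rule also lets chance decide which outcomes are reported as crossover comparisons and which as small parallel-group ones.

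**Working it through.** **Inputs from the documents.** Lens test at two-sided 0.05 (protocol 5.2 and SAP); pre-test at 0.10 (SAP); 24 completers with equal allocation, so 12 per sequence; effects of 6 letters (high contrast, n=24) and 11 letters (low contrast, n=15); 80% power (protocol 5.2).

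**The plan's own figures.** Enrolment reproduces: 24/(1−0.20) = 30. The 24 and 15 cannot be checked independently because no SD is given. Solving the paired t-test for 80% power gives:
- n=24: standardized difference 0.597, so SD of the paired difference = 6/0.597 ≈ 10.0 letters.
- n=15: standardized difference 0.778, so SD = 11/0.778 ≈ 14.1 letters.

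**Assumptions.** Normal data, equal variances, no period effect, and a correlation ρ between a subject's two periods. The documents do not give ρ, so I vary it from 0 to 0.9.

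**Link between the two stages.** The correlation between the period-one contrast and the subject-average contrast is √((1+ρ)/2). The both-period lens contrast is uncorrelated with the average, so it keeps its 0.05 level in unflagged trials. Hence:

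Type I error ≈ 0.10 × P(period one rejects, given a flag) + 0.90 × 0.05.

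As ρ approaches 1 the two between-subject tests coincide. P(rejects, given a flag) then tends to 0.05/0.10 = 0.50, and the total to 0.050 + 0.045 = 9.5%.

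**Simulation, no lens effect and no carry-over** (300,000 trials per row: two-sample t on averages at 0.10; if flagged, two-sample t on period one at 0.05; otherwise paired test at 0.05):

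| ρ | √((1+ρ)/2) | False positives when flagged | By formula | Simulated overall |
|---|---|---|---|---|
| 0 | 0.71 | 24.0% | 6.9% | 6.8% |
| 0.3 | 0.81 | 31.5% | 7.6% | 7.6% |
| 0.5 | 0.87 | 36.5% | 8.2% | 8.2% |
| 0.7 | 0.92 | 42.0% | 8.7% | 8.6% |
| 0.8 | 0.95 | 45.3% | 9.0% | 9.0% |
| 0.9 | 0.97 | 48.5% | 9.3% | 9.4% |

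Always using both periods gives 4.9% to 5.0%. Adjusting the crossover test for period changes none of these results materially.

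**Power with a true 6-letter effect.** Both periods: 80%. Two-stage rule: 0.90 × 0.80 + 0.10 × 0.50 = 77%, and simulation gives 77% at every ρ. Power given a flag is 50% to 53%. For reference, a 12 v 12 period-one test has standardized difference 0.597 × √(2(1−ρ)). Unconditionally its power is 38% (ρ=0.3), 29% (0.5) or 19% (0.7). At ρ=0.5 it would need about 90 subjects in total for 80% power.

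**What the pre-test detects.** A true differential carry-over of 3 letters (half the planned effect) is flagged in 13% of trials at ρ=0.5 and 11% at ρ=0.8. One of 6 letters is flagged in 21% and 14%. The false-flag rate is 10%.

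**Several outcomes.** As an illustration, six independent outcomes each pre-tested at 0.10 give at least one false flag with probability 1 − 0.9⁶ = 47%. Outcomes on the same subjects are correlated, so the true figure will differ.

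**The case against.** Several points on the other side have weight.

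- **The average power loss is small.** It is about 3 points. The 38%, 29% and 19% figures describe a period-one design used unconditionally; given a flag, power is about 50%. Low-contrast acuity has room to spare: with 24 subjects and the 14.1-letter SD, power drops from about 95% to 91%. This stands, and the main fault is the error rate.
- **The inflation arises only through flagged outcomes.** The documents do not show whether any outcome was flagged. If none was, the reported both-period results are already what the fix asks for. The rule's long-run error rate is still not 5%.
- **Dropping the rule leaves real carry-over uncontrolled.** No washout is listed, and lens 2 is fitted at the lens 1 outcome visit (protocol 8.1 and 10.3). With no lens effect and a 3-letter carry-over, the both-period test rejects in about 10% of trials; the two-stage rule does worse, at 12% (ρ=0.5) to 14% (ρ=0.8). At 6 letters the both-period test rejects in 26%, and the two-stage rule in 24% at ρ=0.5 and 26% at ρ=0.8. So the rule helps slightly only against a carry-over as large as the planned lens effect, at low to moderate correlation.
- **The SAP reads as a record of finished work.** It is dated 20 Dec 2021 and uses the past tense, so removing the rule now is a post-hoc change. That is fair, and it calls for disclosure.

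**Conclusion.** The concern holds. With no carry-over and no lens difference, the SAP's rule has a type I error of 6.8% to 9.4% against the stated 5%. The excess comes entirely from outcomes flagged by chance, where 24% to 48% of tests are false positives. Overall power falls from 80% to about 77%, with about 50% in the flagged branch. The rule gives almost no protection against a modest carry-over.

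The sizes rest on 12 completers per sequence, normal data, p<0.10 as the trigger, and an assumed correlation of 0 to 0.9. The power figures also use the back-solved 10-letter SD. The direction does not depend on the correlation: type I error exceeded 5% at every value tried. Because the rule governs the primary endpoint, it needs to be corrected.

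**What to change.** Remove the pre-test and the period-one rule. For every outcome, make the both-period within-subject analysis primary, with lens, period and sequence as fixed effects and subject as random. The SAP model lists no period term; adding one leaves power at 80%. Report the sequence contrast with its confidence interval as description, not as a gate. If a period-one comparison is kept, label it a sensitivity analysis and adjust it for the Visit 1 value where that was collected.

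State openly that negligible carry-over is a design assumption. The support is that the lenses are daily disposable, the protocol does not expect carry-over, and the visit windows put Visit 5 at least 6 days after Visit 3 (day 18 at the earliest against day 12 at the latest). The absence of a listed washout should be acknowledged, and the case made separately for acuity, comfort and tear LTB4.

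If analysis is complete, say which outcomes were flagged, report both-period results for them beside the period-one results, and describe the change as post hoc. If none was flagged, say so.

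The cost is revised SAP text plus a re-run for any flagged outcome and for the added period term. No new data are needed. The remaining price is reliance on the design to exclude carry-over.
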